4.3 Number of Participants

62

4.4 Expected Duration of Study

3 years

5. STUDY TREATMENTS**5.1 Treatment Arms**

Following our meta-analysis of CCT in MCI, showing clear evidence of efficacy on general cognition and psychosocial function¹⁷, clinical equipoise for CCT is shifting in favour of a general recommendation for this intervention (Neurology guidelines; US Taskforce). Accordingly, a purely inactive comparison group is no longer justifiable. Reflecting this, both our treatment arms include the same 3-month/24 session CCT prescription and dose, with only the timing of intervention distinct.

5.1.1 Description**CCT period**

Will utilise the NHMRC-funded Maintain Your Brain Trial's "Brain Training System (BTS)", designed by [name] that implements exercises from NeuroNation. BTS CCT involves online, guided, drill-and-practice standardised tests that load on specific cognitive processes. These cognitively challenging tasks usually are conducted without explicit instruction of problem-solving strategies. The exercises target either working memory, logic, attention and verbal skills or a combination. The BTS system is a personalised cognitive training program run as flash files meaning that the training regime is based on the participants' baseline cognitive profile and continues to evolve in response to within-training task performance. Performance across verbal executive, speed, verbal memory, visual executive, visual memory and visual attention are ranked in descending order. The training session will 'sandwich' the weaker cognitive abilities in the middle of the training session with the participants stronger cognitive task at the beginning and end of the session. Task difficulty and task type will be recalculated throughout the training depending on the participants' improvement. BTS is therefore designed to be automatically adaptive to a participant's baseline score and progress during training.

Participants will complete supervised, group- and centre-based BTS CCT twice a week, one hour each session, for a total of twelve weeks (24 sessions). It will be optional for participants to complete one session per week from home after completing successfully 6 supervised sessions. Each session is 45 minutes long and will comprise of 17 exercises.

Wait list control period

Will comprise of treatment as usual in our referring clinics which comprises psycho-education.

5.1.2 Dosage and Route of Administration

As above

5.1.3 Dosage modification

n/a

5.2 Preparation and administration of study drug

n/a

5.2.1 Dispensing and Product Accountability

n/a

5.3 Measurement of participant compliance

Automated logs of exercises performed by each participant will be created by the BTS after each session.

5.4 Excluded medications and treatments

Participants currently undertaking any 3rd generation antidepressants that are SSRIs or tricyclic antidepressants and with current symptoms of depression, and those currently undertaking other CCT program(s).

6. PARTICIPANT ENROLMENT AND RANDOMISATION**6.1 Recruitment**

62 older adults diagnosed with multi-domain amnesic MCI with sleep disturbance will be recruited from the Healthy Brain Ageing Clinic, Brain and Mind Centre and POWH Memory Clinic in a rolling fashion. The clinics accept referrals from neurologists, geriatricians and psychiatrist as well as local GPs for aged individuals who report new onset cognitive problems. Most of the baseline tests will be taken as part of standard clinic assessment; accordingly, these data will need to have been collected within the last 6-months in order to be valid for study entry.

6.2 Eligibility Criteria**6.2.1 Inclusion Criteria**

- Multi-domain amnesic MCI with sleep disturbance
- Amnesic features defined by impairment in recall tasks.
- Other cognitive domains impairment on representative neuropsychological tests

- Sleep disturbance as measured by the Pittsburgh Sleep Quality Index (PSQI)²⁰ score of ≥ 5
- If using Hypnotics, sedating antihistamines, antipsychotics etc for sleep medication, use must be stable for 3-months (any changes in sleep medication will be monitored during intervention and followup)

6.2.2 Exclusion Criteria

- History of dementia of any aetiology
- History of stroke in last 12 months
- Major neurological disorder requiring current treatment (e.g. epilepsy, Parkinson's disease)
- Major psychiatric disorder requiring current treatment (e.g. schizophrenia, bipolar disorder)
- Current major depression as measured by the 15-item Geriatric Depression Scale (score of ≥ 10) or the 17-item Hamilton Rating Scale for Depression (score of ≥ 12)
- Physical (sensory or motor) impairment that would restrain training
- Current alcohol dependence or abuse
- Currently undertaking external computerised cognitive training and unwilling to cease during trial engagement

6.3 Informed Consent Process

After a participant has been referred to us from a clinic a member of the study team will go through the participant information sheet in person and ensure we have obtained free, fully-informed written consent.

6.4 Enrolment and Randomisation Procedures

Following informed consent, the participant's baseline cognitive data from the referring clinic will be collated and checked for completion. Any additional baseline assessments that are not obtained from the referral clinic will be completed and after all baseline data has been collected the statistician will then inform randomisation status (Arm A or Arm B) to the study co-ordinator (by email) who will then book the participant for the appropriate training schedule.

6.5 Blinding Arrangements

This is a double-blind RCT. Subjects will be informed they will undertake a series of different combination of "brain exercises" of different intensities and will therefore be blind to study hypotheses; expectancies should therefore be well matched. We achieved equivalent insight as to effective treatment status in our NHMRC-funded SMART trial²⁶ between intervention and control groups using this approach. Assessors will be blinded to group status.

NB: As this is a behavioural intervention with no documented risk of adverse events, there are no pre-specified stopping rules or conditions.

6.6 Breaking of the Study Blind

6.6.1 On Study

The participant will continue in the trial as per normal. The person's data will be red-flagged on final analysis, with sensitivity analyses to determine whether they are influencing study outcomes. Please refer to 9.6 for unblinding in the case of adverse events.

6.6.2 Following Completion of the Study

This will be documented but eventually will have no impact on the trial integrity or analysis

6.7 Participant Withdrawal

6.7.1 Reasons for withdrawal

In our experience across four RCTs, the main reasons for study withdrawal are: excessive time commitment, changes in personal circumstances (e.g., illness, relocation) and loss of interest in the program.

The only foreseeable circumstance for early termination of the entire study would be some major infrastructure failure at the study site. In this case, the Chief Investigator [name] will be responsible for informing participants, corresponding to HREC, compiling a final study report, and unbinding if applicable.

6.7.2 Handling of withdrawals and losses to follow-up

The trial co-ordinator ([name]) will be responsible for documenting withdrawals and losses to follow-up.

6.7.3 Replacements

There will be no replacements for withdrawals or loss to follow up.

6.8 Trial Closure

At the close of the trial there will be no ongoing follow-up of trial participants.

6.9 Continuation of therapy

We will provide all participants with advice on whether or not to engage in ongoing computerised cognitive training after the close of the trial, depending on the scientific results of the trial.

7. STUDY VISITS AND PROCEDURES SCHEDULE

List procedures	Enrolment	Baseline	Followup 1 (3 months)	Followup 2 (6 months)	Followup 3 (9 months) Final study visit
Informed consent	✓				

Inclusion/exclusion criteria	✓	✓			
Demographic data		✓			
Neuropsychological examination		✓	✓	✓	✓
Saliva sample		✓			
Actigraphy		✓	✓	✓	
Sleep diary		✓	✓	✓	✓
GARP (Tea and Cookies)		✓	✓		
WHO-QOL		✓	✓	✓	✓
GDS		✓	✓	✓	✓
Amsterdam IADL		✓	✓	✓	✓
Adverse event and serious adverse event logbook			✓	✓	✓

8. CLINICAL AND LABORATORY ASSESSMENTS

Primary Outcome Measure

Global Cognition as defined by pre-specified average of z-scores (referenced to baseline) across following weighted cognitive domains:

1. *Memory (40%)*: Wechsler Adult Intelligence Scale (WAIS) Digit Span²⁴; LOGOS; Wechsler Memory Scale-III Logical Memory I²⁶ and II²⁷, Rey Complex Figure Test-3 minute Recall²⁸.
2. *Speed of processing (15%)*: Trails Making A²⁹.
3. *Language (15%)*: Controlled Oral Word Association Test³¹
4. *Visuospatial skills (15%)*: Rey Complex Figure Test-Copy³¹
5. *Executive functioning (15%)*: Trails Making B²⁹

Secondary Outcome Measures

[figure not shown]
1. Individual cognitive domains measured in separate summary z-score composites
2. Daily functional: Amsterdam IADL
3. Quality of life: WHOQOL
4. Mood and mental-health symptoms: 15-Item GDS
5. Sleep-wake patterns: Sleep diary, actigraphy, PSQI
6. Generalised Axiom of Revealed Preferences (GARP⁴¹)
7. Predictors of responsivity: APOE 3/4 and BDNF ValMet polymorphism, baseline cognitive profile and any other baseline descriptor.

Salival DNA Extraction Swabs Protocol

[figure not shown]
A saliva sample will be collected during baseline measurements to examine APOE4 and BDNF ValMet genotype status. DNA samples will be stored in [name] and analyses will be conducted in [name],

[name] by [name]. BDNF Val/Met polymorphism (rs6265) will be analysed using the Taqman SNP BDNF-AS Assay (SNP ID: rs6265).

[figure not shown]
Oragene•DNA (OG-500)

1. Spit into funnel until the amount of liquid saliva (not bubbles) reaches the fill line shown in picture #1.

[figure not shown]
4. Use the small cap to close the tube tightly.

2. Hold the tube upright with one hand. Close the funnel lid with the other hand (as shown) by firmly pushing the lid until you hear a loud click. The liquid in the lid will be released into the tube to mix with the saliva. Make sure that the lid is closed tightly.

5. Shake the capped tube for 5 seconds. Discard or recycle the funnel.

3. Hold the tube upright. Unscrew the funnel from the tube.

Sleep Actigraphy

An actigraphy watch will be used to measure sleep-wake patterns for one week at baseline, follow-up 1 and follow-up 2. Participants will also complete a sleep diary over this period. Data from Actiwatch systems (Philips, Respironics, USA) will be collected over 30-second epochs and sleep-wake detection scored using Actiware (Philips, Respironics) software. Data will be scored by visual inspection, in conjunction with information from sleep diaries. Wake after sleep onset (WASO) will be identified by epochs of limb movement (specifically non-dominant arm) during the nocturnal rest period, also with reference to light exposure where appropriate. The key variable of interest for this study will be WASO, as per our prior work²⁷. However, we will also record mean sleep onset and sleep offset times, and total sleep time for descriptive purposes. This analysis will be conducted by AI [name].

9. ADVERSE EVENT REPORTING

Adverse event reporting for clinical trials involving therapeutic products, must meet the requirements of the National Health and Medical Research Council, Australian Health Ethics Committee (AHEC) Position Statement “*Monitoring and reporting of safety for clinical trials involving therapeutic products*” (May 2009), which can be found at:

http://www.nhmrc.gov.au/health_ethics/hrecs/reference/files/090609_nhmrc_position_statement.pdf

9.1 Definitions

Device Adverse Events

An adverse event for devices is any undesirable clinical occurrence in a participant whether it is considered to be device related or not, that includes a clinical sign, symptom or condition and/or an observation of an unintended technical performance or performance outcome of the device.

For devices is any adverse medical occurrence that:

- led to a death;
- led to a serious deterioration in health of a patient user or other. This would
- include:
- a life threatening illness or injury;
- a permanent impairment of body function or permanent damage to a body structure;
- a condition requiring hospitalisation or increased length of existing hospitalisation;
- a condition requiring unnecessary medical or surgical intervention; or
- foetal distress, foetal death or a congenital abnormality/birth defect;
- might have led to death or a serious deterioration in health had suitable action or intervention not taken place.
- This includes: a malfunction of a device such that it has to be modified or temporarily/permanently taken out of service; or a factor (a deterioration in characteristics or performance) found on examination of the device.

9.2 Assessment and Documentation of Adverse Events

Adverse events can be reported by participants to the Trial Co-ordinator at any time. She will make an immediate determination whether it is a serious adverse event (SAE) or not. In the case of SAE these will be reported immediately to the Chief Investigator who will manage the event. Specific eliciting for adverse events will occur at each of the follow-up assessments (3 months, 6 months, 9 months). All elicited and non-elicited adverse events will be databased.

9.3 Eliciting Adverse Event Reporting

As noted above, eliciting of adverse event information will occur at each of the follow-up assessments (3 months, 6 months, 9 months).

9.4 Serious Adverse Event Reporting

9.4.1 SAEs

Definition of Serious adverse event (SAE)

An unforeseen medical event that occurs in the course of clinical research that:

- results in participant death
- is life-threatening to the participant

- requires the inpatient hospitalisation or prolongation of existing hospitalisation for the participant leads to the participant having a persistent or significant disability/incapacity.

9.4.2 SUSARs

Suspected Unexpected Serious Adverse Reaction (SUSAR)

Not relevant to this trial

9.5 Specific Safety Considerations (e.g. Radiation, toxicity)

Not relevant to this trial

9.6 Un-blinding procedures for adverse events

The code for any participant should only be broken by the chief investigator or authorised person if it is absolutely necessary to ascertain the type of treatment given. The code will be documented and held by the statistician, not to be provided beyond the study co-ordinator (who requires this in order to administer the interventions) until the completion of the trial, or if un-blinding is required. Cases/adverse events that are considered serious, unexpected and probably or definitely related to the treatment will be unblinded by [name] (an independent statistician and holder of the randomisation code). Blinding of all assessors who are in direct contact with the participants will be maintained.

Contact for unblinding:

[name]

Senior Statistical Consultant

Stats Central

Mark Wainwright Analytical Centre

UNSW Sydney NSW 2052

[contact]

m: [name]

www.statscentral.unsw.edu.au

10. STATISTICAL METHODS

10.1 Sample Size Estimation

This study is powered on the basis of a relative effect size (RES) on Global Cognition of 0.44 at the end of the Phase I RCT (based on average from our Timecourse Trial⁵ and NHMRC SMART trial⁶). Designate power of 0.80 controlling α at 0.05 translates to a required sample size of N=52 (calculated using G*Power 3.1 based on ANOVA repeated measures within-between interaction test, 2 groups, 2 time-points, within subject autocorrelation =0.4, equivalent effect size of $[\eta^2]=0.22$). A sample of N=62 (rounded up from 61) will be recruited to allow for 15% overall attrition (as per Timecourse Trial extrapolated to 9-months).

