	
 • Phase III: T-test between Arm A vs Arm B at FU3. • Clinical Response Prediction will be addressed by multiple regression examining relationships between baseline predictor variables (i.e; cognitive profile) and cognitive change scores. • Sample Size and Power This study is powered on the basis of a relative effect size (RES) on Global Cognition of 0.44 at the end of the Phase I RCT (based on average from our Timecourse Trial⁵ and NHMRC SMART trial⁶). Designate power of 0.80 controlling α at 0.05 translates to a required sample size of N=52 (calculated using G*Power 3.1 based on ANOVA repeated measures within-between interaction test, 2 groups, 2 time-points, within subject autocorrelation =0.4, equivalent effect size of [v]=0.22). A sample of N=62 (rounded up from 61) will be recruited to allow for 15% overall attrition (as per Timecourse Trial extrapolated to 9-months).
Duration of the study	3 years

GLOSSARY OF ABBREVIATIONS

ABBREVIATION	TERM
CCT	Computerised Cognitive Training
MCI	Mild Cognitive Impairment
BTS	NHMRC Maintain Your Brain Trial Brain Training System
ADCS-ADL	Alzheimer’s Disease Cooperative Study-Activities of Daily Living
WHOQOL	World Health Organisation Quality of Life
GDS	Geriatric Depression Scale
PSQI	Pittsburgh Sleep Quality Index
APOE 4	Apolipoprotein E 4
BDNF	Brain-derived neurotrophic factor

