4.2 Study Design

This clinical trial adheres to the conceptual and ethical framework for prevention trials articulated by Peters et al, in which long-term intervention in individuals at-risk for dementia should be correspondingly low-risk²¹. Our experience across four major longitudinal RCTs of CCT has been of no adverse events.

MCI clients that meet basic entry criteria will be recruited from the Healthy Brain Ageing (HBA) clinic, Brain and Mind Centre, University of Sydney (head: [name]) and the Memory Clinic of the Prince of Wales Hospital (head: [name]). Any additional assessments required beyond clinic-based tests, and all intervention procedures, will take place at the Brain and Mind Centre, Sydney, Australia.

The study will consist of three phases and follow-up assessments designed to produce distinct outcomes (refer to **Figure 3**).

Subjects will be randomly allocated in a 1:1 ratio to either ARM A: immediate intervention or ARM B: delayed intervention. Those in ARM A will commence supervised, centre-based multi-domain CCT twice a week, 1 hour per session for 3 months. The main endpoint at the end of Phase I will be to determine whether CCT can improve cognitive function in comparison to a waitlist control. For ARM A, we hypothesize that CCT will lead to an improvement in global cognition. For ARM B, we hypothesise that there will be no change in cognition or measureable cognitive decline. On the basis of our previous work in the Timecourse Trial⁵ and NHMRC-funded SMART Trial³⁸, our proposal is powered for Phase 1 (baseline-FU1) of the trial.

The endpoint of FU2 is designed to assess the magnitude of effect between immediate intervention versus delayed intervention (see Figure 3 and 4). That is, whether the effect size of CCT for ARM B is equivalent to the effect size of CCT for ARM A. We hypothesise that the effect size for those allocated in ARM A will

be greater than ARM B. This is because, as time progresses, the abnormality rates for cognition and other dementia and AD biomarkers increases, thereby making it more difficult to treat. (Figure 1,2)³⁹

Figure 1

[figure not shown]
[figure not shown]
[figure not shown]

Figure 2

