The endpoint of FU3 will assess the long-term implication of immediate compared to delayed intervention. If over a 9-month period the timing of a 3-month CCT intervention does not matter, i.e., both arms are cognitively equivalent at the end, then that may influence and inform the distribution of CCT resources in clinics and the community.

Figure 3: Study Hypotheses

Hypotheses

es = effect size

e = endpoint

Primary

Phase I: $es_{A1} > es_{B1}$

Secondary

Phase II: $es_{A1} > es_{B2}$

Phase III: $e_{A3} = e_{B3}$

Assess for eligibility:
Multi-domain MCI criteria
Sleep disturbance criteria
No major neurological/psychiatric/mood disorder

Exclude:
Not meet inclusion criteria
Declined to participate

Written Consent

Enrolment

Baseline Measurements:

- Neuropsychological tests
- Sleep-wake quality
- DNA saliva swab
- Economic decision making

Randomised (n=62)

ARM A
(n=32)

Allocation

ARM B
(n=32)

- Neuropsychological outcomes
- Sleep-wake quality
- Neuroimaging
- Economic decision making
- Review for any adverse events
- Lost to follow-up (reasons)

Follow-up 1
3-months after baseline

- Neuropsychological outcomes
- Sleep-wake quality
- Neuroimaging
- Economic decision making
- Review for any adverse events
- Lost to follow-up (reasons)

- Neuropsychological outcomes
- Sleep-wake quality
- Review for any adverse events
- Lost to follow-up (reasons)

Follow-up 2
6-months after baseline

- Neuropsychological outcomes
- Sleep-wake quality
- Review for any adverse events
- Lost to follow-up (reasons)

- Neuropsychological outcomes
- Sleep-wake quality
- Review for any adverse events
- Lost to follow-up (reasons)

Follow-up 3
9-months after baseline

- Neuropsychological outcomes
- Sleep-wake quality
- Review for any adverse events
- Lost to follow-up (reasons)

- Intention-to-treat analyses: Linear Mixed Model
- Clinical response prediction: Multiple regression
- Excluded from analysis (reasons)

Analysis

- Intention-to-treat analyses: Linear Mixed Model
- Clinical response prediction: Multiple regression
- Excluded from analysis (reasons)

Screening

MCI criteria

MCI is diagnosed according to the Winblad et al 2004 criteria²² confirmed on the basis of consensus rating of multiple clinicians within the memory center.

Typically, this includes a geriatrician or neurologist and two clinical neuropsychologists who review the individual's clinical profile and neuropsychological results.

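### The sample size enters an interaction effect twice as large as the stated effect of 0.44 implies, so the claimed 80% power for the primary endpoint is really about 30%

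*Protocol*

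**What the plan says.** Section 10.1 sets the target effect: "This study is powered on the basis of a relative effect size (RES) on Global Cognition of 0.44 at the end of the Phase I" trial, taken as an average from two earlier trials. It then gives the result, "Designate power of 0.80 controlling α at 0.05 translates to a required sample size of N=52", and the method, "calculated using G*Power 3.1 based on ANOVA repeated measures within-between interaction test, 2 groups, 2 time-points, within subject autocorrelation =0.4". The synopsis repeats the calculation and gives the converted input as "equivalent effect size of [v]=0.22". Section 10.1 attaches the same 0.22 to an eta-squared symbol, though either symbol may have been altered when the text was read from the PDF. The 52 is raised to 62 for 15% attrition.

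Section 10.3 makes the same term the primary test: a linear mixed model with Group, Time (baseline and follow-up 1) and their interaction, with covariates only if the arms are seen to differ at baseline. Section 4.2 sets 1:1 allocation and confirms that the trial is powered for Phase I.

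**The concern.** The value 0.22 is exactly half of 0.44. Dividing d by two is the usual conversion to Cohen's f when two group means are compared once. The procedure named here tests a different quantity, the interaction in a table of two groups by two times, where the same difference is spread over four cells. If the two-group conversion was entered into the interaction procedure, the calculation assumes twice the stated effect.

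This is the only justification given for the sample size, and it concerns the primary outcome. If power is about 30%, the trial would miss its own assumed effect roughly seven times in ten. A reader who trusts the stated 80% could then take a null Phase I result as evidence against the training.

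**Working it through.** **Inputs.** Relative effect size (RES) 0.44; converted value 0.22; alpha 0.05; power 0.80; k = 2 groups; m = 2 time points; correlation rho = 0.4; N = 52; attrition 15% (all Section 10.1). Allocation is 1:1 (Section 4.2). Assumption: RES is a between-arm difference in change, or an end-of-phase difference with equal baselines, in SDs of the score. The protocol does not define it.

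**1. Reproduce the plan's figure.** G*Power's default option for this test uses a noncentral F with

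lambda = f² × N × m / (1 − rho), df = 1 and N − 2.

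With f = 0.22 and N = 52: lambda = 0.0484 × 52 × 2 / 0.6 = 8.39, power 0.811. N = 50 gives 0.795. The smallest equal-arm total is therefore 52, as stated. For attrition, 52 / 0.85 = 61.2, which rounds up to 62; that step is correct.

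Other meanings of 0.22 do not give 52. As eta-squared, f = √(0.22/0.78) = 0.531 and N = 12. Under G*Power's SPSS and Cohen effect-size options, N = 168 and 166. So 0.22 was almost certainly entered as f.

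**2. Convert 0.44 to f for the interaction.** Put the four cell means at Arm A 0 then 0.44, and Arm B 0 then 0. The grand mean is 0.11, the Arm A mean 0.22 and the follow-up mean 0.22. The interaction deviation of the Arm A follow-up cell is

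0.44 − 0.22 − 0.22 + 0.11 = 0.11,

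and the other three cells are ±0.11. Hence f = 0.44 / 4 = 0.11.

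The change scores confirm it. Their variance is 2(1 − rho) = 1.2, so the contrast gives

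lambda = RES² × N / (8(1 − rho)) = 0.1936 × 52 / 4.8 = 2.10.

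Equating this with the formula in step 1 gives f = RES / 4. Conversely, f = 0.22 requires a difference in change of 4 × 0.22 = 0.88 SD.

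**3. Power at the stated effect (0.44, rho = 0.4, alpha 0.05).**

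| Quantity | Result |
|---|---|
| Power, N = 52 | 0.295 (simulation 0.297) |
| Power, N = 62, no attrition | 0.343 |
| N for 80% power | 198 evaluable (196 gives 0.799) |
| Recruited N with 15% attrition | 198 / 0.85 = 232.9, so 233 (234 for equal arms) |
| Effect detectable with 80% power, N = 52 | 0.87 SD |
| Same, baseline-adjusted | 0.73 SD |

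**4. Sensitivity at N = 52.**

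| Change to the inputs | Power |
|---|---|
| rho = 0.5 | 0.34 |
| rho = 0.6 | 0.41 |
| rho = 0.7 | 0.52 |
| rho = 0.8 | 0.69 |
| rho = 0.85 | 0.81 |
| Follow-up 1 scores only, d = 0.44 | 0.34 |
| 0.44 in SDs of the change score | 0.34 |
| Baseline-adjusted, rho = 0.4 | 0.40 |
| One-sided alpha 0.05 | 0.42 |

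**The case against.** The strongest objection is that RES is undefined and comes from trials that are not at hand, so 30% is conditional on a reading. One alternative deserves a test. Section 8 defines global cognition as a weighted average of z-scores and does not say that the average is re-standardised, so its SD would be below 1. If 0.44 were in those units, the standardised effect would be larger. Take the Section 8 weights, split the 40% for memory equally over its five tests, and assume one common correlation r between tests. The variance is then 0.122 + 0.878r, because the squared weights sum to 5 × 0.08² + 4 × 0.15² = 0.122. For r from 0.2 to 0.5 the SD is 0.55 to 0.75, the effect 0.80 to 0.59, and power at 52 is 0.73 to 0.47. It would reach 0.80 only if r fell to about 0.15. This reading also fits poorly with a quantity called an effect size and converted by halving. It shows that 30% depends on the definition; it does not restore the claim over that range.

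A second objection is that Arm B may worsen: "For ARM B, we hypothesise that there will be no change in cognition or measureable cognitive decline". That allows a difference above 0.44, but 0.88 would need Arm B to fall by 0.44 SD in three months while Arm A gains 0.44. The protocol nowhere assumes this, and a relative effect would ordinarily already be net of control.

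Two smaller points stand. That 0.22 is f is inferred from reproducing 52, since the printed symbols say otherwise. And the protocol does not itself say how a null result would be interpreted, so the risk of misreading it is a judgement.

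**Conclusion.** The concern holds. The arithmetic that follows the conversion is correct; the conversion is wrong by a factor of two, which is a factor of four in the noncentrality (8.39 against 2.10). For the effect the protocol names, with its own correlation and test, power is about 0.30 at 52 evaluable and 0.34 at 62, against the stated 0.80. The design has 80% power only for a difference of about 0.87 SD.

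This rests on reading RES as a standardised between-arm difference and 0.22 as Cohen's f. The first is the natural reading, and the second is the only one tested that returns 52. Post-only, change-score, baseline-adjusted and one-sided versions give 0.34 to 0.42. A higher correlation rescues the claim only near 0.85, far from the 0.4 the protocol fixes. The calculation is stated in full in the protocol, so this is an error in what is written and not detail left to a separate analysis plan.

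**What to change.** Keep 62 and amend Section 10.1 and the synopsis together:

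- Define RES and name the effect-size symbol identically in both places.
- State that RES 0.44 corresponds to f = 0.11 for the Group x Time interaction, and delete the claim of 0.80 power at 0.44.
- State that with 52 evaluable and correlation 0.4, power is about 30% for the Group x Time test, or about 40% with baseline adjustment, and that 80% power is available only for about 0.87 SD (0.73 SD baseline-adjusted). The adjusted figures apply only if Section 10.3 specifies that adjustment in advance; at present it makes covariates conditional on observed baseline differences.
- State that a non-significant Phase I result is inconclusive and will be reported with its 95% confidence interval.
- In the same amendment, correct the flow chart in Figure 3, which shows 32 per arm (64 in total) against 62 randomised; 1:1 allocation gives 31 per arm.

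If the sponsor meant something else by RES, or has grounds for a larger effect or a higher correlation, the amendment should say so and show the recalculation. The cost is a wording amendment: no extra participants, but a less favourable stated power.
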